### 8.4.3 Power analysis

Per the weekly adherence percentage outcome, standardized effect sizes (mean difference divided by a pooled SD) greater than 0.2 will be detected by the mixed effects linear models regardless of magnitude of within-subject outcome correlations over time.

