## 11.4 Sample Size Determination

Sample size N=300 per arm, or a total of N=600, was determined based on feasibility of recruitment from all sites during the study period. Power analysis for each hypothesis below is conservatively conducted based on a reduced sample size (N= 270 per arm, or N=540 in total) after considering 10% attrition rates. The target power is 80% with a two-sided significance level of 0.05. To this end, minimally detectable effect sizes and widths of 95% confidence intervals were computed with those parameters and the sample size after attrition.

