### **Power analysis: Minimally detectable effect sizes**

**SVR:** Considering the base 80% SVR rate of in PN arm, a minimum of 9% difference between the two arms will be detected (i.e., 89% vs. 80%, Odds Ratio (OR)=2.1) in a multivariable logistic regression model in which confounding variables will explain 10% of variation in the predictor variable. This study posits that a >9% difference in SVR between the PN and mDOT groups will be clinically significant based on studies that showed that SVR in treatment naive patients was >90% [14].

Mixed effects logistic regression models for the undetectable HCV load will be able to detect even smaller percent point difference since they will utilize repeated measures for each subject no matter how large within-subject outcome correlations will be.

**Treatment initiation rate:** With anticipated 60% treatment initiation rate in the mDOT arm, a minimum of 7% difference will be detectable (i.e., 60% vs. 67%, OR=0.74) in any outcome in a multivariable logistic regression model in which confounding variables will explain 10% of variation in the predictor variable. Note that sample size for this analysis will be N=1000, the total number of randomized participants.

**Adherence rate:** With expected 80% adherence rate in the PN arm, a minimum of 9% difference in adherence rates between the 2 arms will be detectable (i.e., 89% vs. 80%, OR=2.1) in a multivariable logistic regression model. Per the repeatedly measured continuous adherence percentage outcome, mixed effects linear models will be able to detect standardized effect sizes (mean difference divided by a pooled Standard

Deviation (SD)) greater than 0.2 irrespective of magnitudes of within-subject outcome correlations over time. In a previous DOT study, a standardized effect size of mDOT vs. TAU was estimated to be 0.6.

**Treatment completion rate.** Under the expected 80% completion rate in the PN arm, a minimum of 9% difference in completion rates between the two arms will be detectable (i.e., 89% (mDOT) vs. 80% (PN), OR=2.1).

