### 3.3 Per protocol analytic sample

This per protocol (PP) analytic sample includes the enrolled study participants who 1) were randomized; 2) initiated treatment; 3) complied with the randomly assigned models of care without cross over any time during the 12-week treatment; and 4) had SVR outcome data (yes vs. no). This sample is referred to as the per-protocol (PP) analytic sample. The PP sample will be a subset of the mITT sample which is in turn a subset of the ITT sample.

The intention-to-treat principle reflects the principle that once the intervention was randomly assigned to a participant, the participant's intervention assignment will not change in the analysis even if s/he crossed over the other intervention during the trial period or did not complete intervention activities. The application of this ITT principle reflects the real-world goal of the HERO study which is to treat all PWID with HCV (i.e., all randomized individuals).

However, as the HERO study was designed as of a pragmatic randomized clinical trial (RCT), the ITT sample will not be used as the primary analytic sample because the outcomes are defined conditions on the initiation. Furthermore, the primary (SVR) and several of the other secondary outcomes (treatment completion, adherence) are only relevant among those who initiated treatment.

**All statistical analyses proposed in the present SAP will be repeated for each analytic sample.** Comparison across the three analytic samples will be compared to assess internal or external validities or limitations of the study findings. In particular, analysis of the secondary ITT sample will provide estimates of milestones along the HCV cascade of care by study arm and in the full sample. All statistical analyses will be conducted using SAS v9.4 and R 3.5 or higher, and a two-tailed significance level of 0.05 will be applied to all testing and confidence intervals.

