### 5.5 Power analysis

The HERO study was planned to recruit N=300 participants in each arm in the mITT sample. Considering the base 80% SVR rate in the PN arm, a minimum difference of 9% between the two arms will be detected (i.e., 89% vs. 80%, OR=2.1) with the planned sample size in a multivariable logistic regression model in which adjusting variables explain 10% of variation in the predictor variable. This study posits that a >9% difference in SVR between the PN and DOT groups will be clinically significant based on studies that showed that SVR in treatment naive patients was >90%.

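### The plan says adherence effects above 0.2 SD are detectable at any within-subject correlation; on its own inputs this holds only up to a correlation of about 0.63 (protocol) or 0.72 to 0.74 (SAP)

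*SAP*

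**What the plan says.** SAP 8.4.3, the SAP's only power statement for adherence, takes the standardized effect as the mean difference over a pooled SD and says that effects "greater than 0.2 will be detected by the mixed effects linear models regardless of magnitude of within-subject outcome correlations over time". Protocol 11.10, under the minimally detectable effect for adherence, likewise gives effects "greater than 0.2 irrespective of magnitudes of within-subject outcome correlations over time". Neither place states an assumed correlation or a formula.

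The design inputs are given elsewhere. Protocol 11.4 says "The target power is 80% with a two-sided significance level of 0.05" and works with 270 per arm after 10% attrition. SAP 3.3 says "a two-tailed significance level of 0.05 will be applied to all testing and confidence intervals". SAP 5.5 says "The HERO study was planned to recruit N=300 participants in each arm in the mITT sample". The statistical model in Protocol 11.10 has a random subject intercept and 6 post-baseline time points. SAP 8.4 uses weekly or biweekly blister-pack rates, which is 12 or 6 values per person over 12 weeks of treatment.

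**The concern.** When two arms are compared on the average of several measurements per person, the gain from repeating the measurement depends on how alike those measurements are. If they are nearly identical within a person, the repeats carry almost no new information and the design is worth one measurement per person. A threshold said to hold at every correlation must therefore hold in that limiting case, and 0.2 SD looked too small for 270 or 300 per arm.

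What is at stake is how a null adherence result is read. A reader who takes the sentence at its word could conclude that effects just above 0.2 SD had been given 80% power, when that depends on a correlation that the plan does not state.

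**Working it through.** **Inputs.** Two-sided 0.05 (Protocol 11.4, SAP 3.3). 80% power (Protocol 11.4; SAP 8.4.3 gives no power level of its own). n per arm = 270 (Protocol 11.4) or 300 (SAP 5.5). m = 6 (Protocol 11.10), or 6 or 12 (from SAP 8.4). Equal allocation (Protocol 5.4). The random intercept gives the same correlation ρ between any two time points.

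**Formulas.** With the SD of a single measurement as the unit, the standard error of the arm difference is

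SE = √[(2/n) × (1 + (m − 1)ρ)/m].

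The detectable effect is (1.960 + 0.842) × SE, and power at 0.2 SD is Φ(0.2/SE − 1.960).

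**The plan's own figure.** At ρ = 1 the factor (1 + (m − 1)ρ)/m equals 1 whatever m is:
- 270 per arm: 2.802 × √(2/270) = 2.802 × 0.0861 = 0.241 SD
- 300 per arm: 2.802 × √(2/300) = 2.802 × 0.0816 = 0.229 SD

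Both become 0.2 at one decimal; neither is 0.20. The continuous-outcome figures in the subgroup power paragraph of Protocol 11.10 follow the same pattern. A total of 270 (135 per arm) gives 0.341, printed as 0.3. A total of 108 (54 per arm) gives 0.539, printed as 0.5. The 0.2 therefore looks like the ρ = 1 value printed to one decimal.

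**Where 0.20 SD holds.** Setting the detectable effect to 0.2 gives ρ = (mF − 1)/(m − 1), where F = (0.2 / detectable effect at ρ = 1)²:
- 270 per arm: F = 0.688. With m = 6, ρ = (4.128 − 1)/5 = 0.63. With m = 12 it would be 0.66.
- 300 per arm: F = 0.764. With m = 6, ρ = (4.587 − 1)/5 = 0.72. With m = 12, ρ = (9.173 − 1)/11 = 0.74.

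**Detectable effect (SD) and power at 0.2 SD, by correlation.**

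| ρ | 270 per arm, m = 6 | 300 per arm, m = 6 | 300 per arm, m = 12 |
|---|---|---|---|
| 0.5 | 0.184; 86% | 0.175; 89% | 0.168; 91% |
| 0.7 | 0.209; 77% | 0.198; 81% | 0.195; 82% |
| 0.8 | 0.220; 72% | 0.209; 77% | 0.207; 77% |
| 0.9 | 0.231; 68% | 0.219; 73% | 0.218; 73% |
| 1 (limit) | 0.241; 64% | 0.229; 69% | 0.229; 69% |

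**Size needed for the sentence to be true.** Detecting 0.2 SD at any ρ needs n = 2 × 2.802²/0.2², or 393 per arm.

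**Variants, at ρ = 1.**
- A t-based calculation gives 0.242 (270 per arm) and 0.229 (300 per arm).
- Covariates explaining 10% of the arm variable, as the plan assumes for SVR, raise the values to 0.254 and 0.241.
- A one-sided 0.05 test at 300 per arm gives 0.203, but both documents specify two-sided testing.
- If all 375 + 379 = 754 participants in the column headings of SAP Table 1 counted as initiators (377 per arm), the value would be 0.204 with 78% power at 0.2 SD. The documents do not give the number of initiators, so this is an upper bound on n.

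**The case against.** The strongest defence is rounding. The protocol gives its continuous effect sizes to one decimal, and 0.229 and 0.241 both print as 0.2. On that view the authors did take the worst case over all correlations, and only a second decimal is missing. This probably explains the figure. It does not make the sentence right, because 0.2 is used as a threshold above which effects will be detected, and rounding down makes the design look more sensitive than it is.

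A second defence is that the pooled SD could be that of each person's average, not of a single weekly value. The correlation then drops out, but the detectable effect is 0.229 or 0.241 SD. On one reading the independence from correlation fails; on the other the 0.2 fails.

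Third, the practical weight is small, and this stands. The outcome is secondary, and Protocol 11.4 sets the sample size by recruitment feasibility, not by this figure. At the 0.6 SD that Protocol 11.10 cites for mDOT against treatment as usual, power exceeds 99.9% at any correlation. The documents give no within-subject correlation, so whether the true value lies above the limits is unknown.

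A reader might also infer the same error in the protocol's sentence on repeated undetectable viral load, where the models are said to "utilize repeated measures for each subject no matter how large within-subject outcome correlations will be". The documents do not support that. The sentence sets no threshold; it claims only a smaller detectable difference than the single SVR comparison. The factor (1 + (m − 1)ρ)/m is below 1 for every ρ below 1, so repeats help, if only slightly when ρ is high. That sentence can stay.

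**Conclusion.** The adherence statement in SAP 8.4.3 and Protocol 11.10 is wrong as an unconditional claim. The shortfall appears only above the correlation limits: at ρ = 0.9, power at 0.2 SD is 7 points (300 per arm) or 12 points (270 per arm) below the 80% target. Below the limits the stated 0.2 SD is met.

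A reader might take 0.23 to 0.24 SD, or 64% to 69% power, as what high correlation generally produces. Those are the values at ρ = 1, where repeats add nothing; at ρ = 0.9 the figures are 0.22 to 0.23 SD and 68% to 73%. Nor do the documents support a conclusion that the trial is underpowered for adherence.

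The result rests on the random-intercept structure named in the protocol, complete data at every time point, the planned sample sizes, and the protocol's 80% target carried over to the SAP. Severity is minor: a stated design property needs correcting, and no analysis depends on it.

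**What to change.** In SAP 8.4.3 and in the adherence paragraph of the power section of Protocol 11.10, do one of two things:

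- State the figure that holds at any correlation: about 0.23 SD with 300 per arm (SAP), or 0.241 SD with 270 per arm (protocol).
- Keep 0.20 SD and add its condition: a within-subject correlation of at most about 0.63 (270 per arm, 6 time points), or 0.72 with 6 and 0.74 with 12 time points (300 per arm).

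In either case SAP 8.4.3 should name the power level, which it now leaves to the protocol. The cost is one sentence in each document and a slightly less favourable figure. Sample size, model, test and analysis sets are unchanged.
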